#### **12.3.2.4 Study Drug Exposure and Compliance**

Study drug exposure will be summarized based on the Safety Set, defined as the last day of study drug in this open-label study minus the first day of study drug in this open-label study plus 1, regardless of study drug interruption. For subjects who enroll in another qualified Vertex study and resume participation in this study, time spent in the other study will be excluded.

Study drug compliance will be summarized based on the Safety Set and will be calculated as:  $100 \times [1 - (\text{total number of days of study drug interruption in this open-label study}) / (\text{duration of study drug exposure in days in this open-label study})]$ . A study drug interruption on a given day is defined as an interruption of any study drug on that day. For subjects who enroll in another qualified Vertex study and resume participation in this study, time spent in the other study will be excluded.

#### **12.3.2.5 Important Protocol Deviations**

An IPD is a deviation that may significantly affect the completeness, accuracy, or reliability of the study data or that may significantly affect a subject's rights, safety, or well-being.

All IPDs will be provided in an individual subject data listing, as appropriate.

#### **12.3.3 Efficacy Analysis**

Not applicable.

#### **12.3.4 Safety Analysis**

All safety analyses will be based on the TE Period in this open-label study for subjects in the Safety Set, unless otherwise specified.

The overall safety profile of study drug will be assessed in terms of the following safety and tolerability endpoints:

- Incidence of treatment-emergent adverse events (TEAEs)
- Clinical laboratory values (i.e., serum chemistry, hematology, coagulation, and urinalysis)
- ECGs
- Vital signs
- Pulse oximetry

All safety data will be presented in individual subject data listings. Only descriptive analyses of safety data will be performed. Additional details will be described in the statistical analysis plan (SAP).

#### **12.3.4.1 Adverse Events**

For analysis purposes, AEs will be classified as pretreatment AEs, TEAEs, or post-treatment AEs, defined as follows:

- **Pretreatment AE:** any AE that occurred since the end of the TE Period in a parent study and before the first dose of ELX/TEZ/IVA in the TE Period in the open-label study. For subjects who depart this study to enroll in another qualified Vertex study and resume participation in this study, details of pre-treatment AEs will be specified in the SAP.
- **TEAE:** any AE that worsened (either in severity or seriousness) or newly developed at or after the first dose date of ELX/TEZ/IVA in the TE Period in this open-label study.
- **Post-treatment AE:** any AE that worsened (either in severity or seriousness) or newly developed after the TE Period in this open-label study.

For AEs with missing or partial start dates, if there is no clear evidence that the AEs started before or after study drug treatment, then the AEs will be classified as TEAEs.

AE summary tables will be presented for TEAEs only and will include the following:

- Overview of TEAEs
- TEAEs
- Related TEAEs
- TEAEs by maximum severity
- TEAEs by strongest relationship
- Grade 3 and Grade 4 TEAEs
- Serious TEAEs
- Related serious TEAEs
- TEAEs leading to treatment discontinuation
- TEAEs leading to treatment interruption
- TEAEs leading to death

Summaries will be presented using frequency counts and percentages (i.e., number and percentage of subjects with an event). When summarizing the number and percentage of subjects with an event, subjects with multiple occurrences of the same AE or a continuing AE will be counted once, only the maximum severity level will be presented in the severity summaries, and the strongest relationship level in the relationship summaries.

Listings containing individual subject level AE data will be provided separately for:

- Serious TEAEs
- Grade 3/4 TEAEs
- TEAEs leading to treatment discontinuation
- TEAEs leading to treatment interruption
- TEAEs leading to death

In addition, all AEs, including pre- and post-treatment AEs, will be presented in individual subject data listings

#### **12.3.4.2 Clinical Laboratory Assessments**

For the TE laboratory measurements, the observed values and change from baseline values of the continuous laboratory parameters will be summarized in SI units at each time point during the TE Period.

For threshold analysis, the number and percentage of subjects with at least 1 threshold event during the TE Period will be summarized. The threshold criteria and selected parameters will be provided in the SAP.

Results of urinalysis and pregnancy tests will be listed in individual subject data listings only. In addition, a listing containing individual subject laboratory assessment values will be provided. This listing will include data from scheduled and unscheduled time points.

Additional safety laboratory data analyses may be described in the SAP.

#### **12.3.4.3 Electrocardiogram**

For the TE ECG measurements, a summary of observed values and change from baseline values will be provided at each time point during the TE Period, for the following ECG interval measurements (in msec): RR, PR, QT, QT corrected for HR intervals (QTcF), QRS duration, and HR (beats per minute).

For threshold analysis, the number and percentage of subjects with at least 1 threshold event during the TE Period will be summarized. The threshold criteria will be provided in the SAP.

Additional ECG analyses may be described in the SAP.

#### **12.3.4.4 Vital Signs**

For the TE vital signs measurements, the observed values and change from baseline values will be summarized at each time point during the TE Period in this open-label study. The following vital signs parameters will be summarized: systolic and diastolic blood pressure (mm Hg), body temperature (°C), pulse rate (beats per minute), and respiratory rate (breaths per minute).

For threshold analysis, the number and percentage of subjects with at least 1 threshold event during the TE Period will be summarized. The threshold criteria will be provided in the SAP.

Additional vital signs analyses may be described in the SAP.

#### **12.3.4.5 Pulse Oximetry**

For the TE pulse oximetry measurements, a summary of observed values and change from baseline values will be provided at each time point during the TE Period, for the percent of oxygen saturation by pulse oximetry.

#### **12.3.4.6 Other Safety Analyses**

Details of other safety analyses may be included in the SAP.

### **12.4 Interim Analysis**

Not applicable

### **12.5 Data Monitoring Committee Analysis**

Not applicable.

## **13 PROCEDURAL, ETHICAL, REGULATORY, AND ADMINISTRATIVE CONSIDERATIONS**

### **13.1 Adverse Event and Serious Adverse Event Documentation, Severity Grading, and Reporting**

#### **13.1.1 Adverse Events**

##### **13.1.1.1 Definition of an Adverse Event**

An AE is defined as any untoward medical occurrence in a subject during the study; the event does not necessarily have a causal relationship with the treatment. This includes any newly occurring event or worsening of a pre-existing condition (e.g., increase in its severity or frequency) after the ICF is signed.

An AE is considered serious if it meets the definition in Section 13.1.2.1.

##### **13.1.1.2 Clinically Significant Assessments**

Study assessments including laboratory tests, ECGs, PEs, and vital signs will be assessed and those deemed to have clinically significant worsening from baseline will be documented as an AE. When possible, a clinical diagnosis for the study assessment will be provided, rather than the abnormal test result alone (e.g., urinary tract infection, anemia). In the absence of a diagnosis, the abnormal study assessment itself will be listed as the AE (e.g., bacteria in urine or decreased hemoglobin).

An abnormal study assessment is considered clinically significant if the subject has 1 or more of the following:

- Concomitant signs or symptoms related to the abnormal study assessment
- Further diagnostic testing or medical/surgical intervention
- A change in the dose of study drug or discontinuation from the study

Repeat testing to determine whether the result is abnormal, in the absence of any of the above criteria, does not necessarily meet clinically significant criteria. The determination of whether the study assessment results are clinically significant will be made by the investigator.

A laboratory value that is Grade 4 will not automatically be an SAE. A Grade 4 laboratory value will be an SAE if the subject's clinical status indicates a life-threatening AE.

### **13.1.1.3 Documentation of Adverse Events**

All AEs will be collected from the time the ICF is signed until the following times:

- For subjects who do not enroll: until time of screen failure (e.g., screen failure, withdrawal of consent)
- For enrolled subjects who have a Safety Follow-up Visit: through the Safety Follow-up Visit
- For enrolled subjects who do not have a Safety Follow-up Visit, the earliest of
  - 28 days after the last dose of study drug, or
  - the ETT Visit, if that visit is 3 weeks or later following the last dose of study drug (see Section 9.1.3)
- For subjects who depart this study to enroll in another qualified Vertex study: through the time of enrollment in another qualified Vertex study
- For subjects who depart this study to enroll in another qualified Vertex study and resume participation in this study, AEs will be collected from the time of the Returning Visit until the subject completes study participation in this study. AEs that fully occur (start and end) in the other qualified Vertex study will be recorded as medical history; AEs that started during participation in the other qualified Vertex study and are ongoing at the time of the Returning Visit in this study will be recorded as AEs in this study.

All subjects or the subjects' parents or legal guardians, as appropriate, will be queried, using nonleading questions, about the occurrence of AEs at each study visit. When possible, a constellation of signs and/or symptoms will be identified as 1 overall event or diagnosis. All AEs for enrolled subjects will be recorded in the CRF and source document. AEs for subjects who are screened but not subsequently enrolled will be recorded only in the subject's source documents.

The following data will be documented for each AE:

- Description of the event
- Classification of "serious" or "nonserious"
- Date of first occurrence and date of resolution (if applicable)
- Severity
- Causal relationship to study drug(s)
- Action taken
- Outcome
- Concomitant medication or other treatment given

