### 8.1 Inclusion Criteria

1. Subject (or his or her legally appointed and authorized representative) will sign and date an informed consent form (ICF) and, when appropriate, an assent form.
2. Willing and able to comply with scheduled visits, treatment plan, study restrictions, laboratory tests, contraceptive guidelines, and other study procedures.
3. Did not withdraw consent from a parent study.
4. Meets at least 1 of the following criteria:
  - Completed study drug treatment in a parent study.
  - Had study drug interruption(s) in a parent study, but did not permanently discontinue study drug, and completed study visits up to the last scheduled visit of the Treatment Period of a parent study.
5. For subjects being considered for resumption of participation in this study after enrolling in another Vertex study of investigational CFTR modulators (referred to as "another qualified Vertex study"): Completed the ETT visit in another qualified Vertex study before or on the same day as the Returning Visit in this study. If more than 30 days have elapsed since the ETT visit in the other qualified Vertex study, approval of the medical monitor is required.
6. Willing to remain on a stable CF treatment regimen (as defined in Section 9.5) through completion of study participation.

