### 9.5 Prior and Concomitant Medications

Information regarding prior and concomitant medications, including CF medications, other medications, and herbal and naturopathic remedies, will be collected in each subject's source documentation for medications taken within the 56 days before the first dose of study drug in this study through completion of study participation, as defined in Section 9.1.5. For subjects who enroll in another qualified Vertex study and resume participation in this study, any new medications started after the subject first departs this study will be collected for the period after the Departing Visit and before study drug dosing resumes in this study, through completion of study participation.

- Subjects should remain on a stable treatment regimen for their CF through completion of study participation. Stable treatment regimen is defined as the current treatment regimen for CF that subjects have been following for at least 28 days before Day 1. Subjects should not

initiate long-term treatment with new medication from 28 days before the Day 1 Visit through completion of study participation. Guidelines for stable treatment regimens for CF are as follows:

- o Subjects who are taking inhaled tobramycin or other chronically inhaled antibiotics should remain on that regimen throughout the study.
- o Subjects who cycle onto and off of an inhaled antibiotic should continue on their prior schedule.
- o Subjects who alternate between 2 different inhaled antibiotics should remain on the same cycling schedule during the study.
- Subjects may receive doses of prednisone or prednisolone of up to 10 mg/day chronically, or up to 60 mg daily for up to 5 days.
- ELX may inhibit OATP1B1 and OATP1B3, which may increase the exposure of medicinal products that are substrates for these transporters. Substrates such as statins, glyburide, nateglinide, and repaglinide should be used with caution.
- IVA is a weak inhibitor of P-glycoprotein (P-gp). Administration of IVA may increase systemic exposure of medicinal products that are sensitive substrates of P-gp, which may increase or prolong their therapeutic effect and adverse reactions. Digoxin or other substrates of P-gp with a narrow therapeutic index, such as cyclosporine, everolimus, sirolimus, and tacrolimus, should be used with caution and appropriate monitoring.

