### **13.1.2.2    Reporting and Documentation of Serious Adverse Events**

All SAEs that occur after obtaining informed consent and assent (where applicable) through completion of study participation, regardless of causality, will be reported by the investigator to Vertex GPS **within 24 hours of identification**. In addition, all SAEs that occur after the Safety Follow-up Visit and are considered related to study drug(s) will be reported to Vertex GPS **within 24 hours of identification**.

For subjects who depart this study to participate in another qualified Vertex study, SAEs will be collected in the same manner as described for AEs (Section 13.1.1.3).

For SAEs that occur after obtaining informed consent and assent (where applicable) through completion of study participation, the SAE Form will be completed for new/initial events as well

as to report follow-up information on previously reported events. Investigators are asked to report follow-up information as soon as it becomes available to ensure timely reporting to health authorities.

Please send completed SAE Forms to Vertex GPS via:

Email: [REDACTED] (preferred choice)

Fax: [REDACTED]

For technical issues related to submitting the form, contact telephone: [REDACTED]

SAEs that occur after completion of study participation and are considered related to study drug(s) will be recorded on the Vertex Clinical Trial Safety Information Collection Form (hereafter referred to as the “SAE Form”) using a recognized medical term or diagnosis that accurately reflects the event. SAEs will be assessed by the investigator for relationship to the investigational study drug(s) and possible etiologies. On the SAE Form, relationship to study drug(s) will be assessed only as related (includes possibly related) or not related (includes unlikely related), and severity assessment will not be required. For the purposes of study analysis, if the event has not resolved at the end of the study reporting period, it will be documented as ongoing. For purposes of regulatory safety monitoring, the investigator is required to follow the event to resolution and report the outcome to Vertex using the SAE Form.

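### For subjects who depart and return, no rule collects or classifies adverse events that start between the other study's ETT visit and the Returning Visit, and the two documents treat that time differently

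*Protocol*

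**What the plan says.** **Collection.** Under Protocol 13.1.1.3, AE collection for a departing subject runs "through the time of enrollment in another qualified Vertex study". For one who comes back, "AEs will be collected from the time of the Returning Visit until the subject completes study participation in this study". Two classes of event bridge the absence. First, "AEs that fully occur (start and end) in the other qualified Vertex study will be recorded as medical history". Second, events that began in the other study and persist at the Returning Visit become AEs of this study. Protocol 13.1.2.2 sends SAEs of departing subjects to the same rule. Table 3-1, by contrast, shows AE collection as unbroken from consent to the end of participation.

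**Length of the interval.** Protocol 9.1.1 lets the other study's ETT visit and the Returning Visit fall on one day. Protocol 8.1, criterion 5, adds: "If more than 30 days have elapsed since the ETT visit in the other qualified Vertex study, approval of the medical monitor is required". No upper limit is given.

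**Analysis.** For exposure and compliance in returners, Protocol 12.3.2.4 states that "time spent in the other study will be excluded", and SAP 9.2.5 and 9.2.6 say the same. Protocol 12.3.1 makes a like exclusion from the TE Period. The TE Period in SAP 9.1 has no exclusion. Protocol 12.3.4.1 leaves returners' pre-treatment AEs to the SAP, and the flag in SAP 9.3.1 covers only events that began in the other study and were ongoing at return.

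**Medications.** Under Protocol 9.5, new medications "will be collected for the period after the Departing Visit and before study drug dosing resumes in this study".

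**The concern.** Safety and tolerability is the only primary endpoint, so AE capture is the endpoint itself. Between the other study's ETT visit and the Returning Visit, a subject belongs to neither study's stated collection window as far as these documents show. An AE or SAE that starts and ends there has no place in Protocol 13.1.1.3. One that starts there and persists may well be noticed at the Returning Visit, but nothing says how to classify it.

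The medication rule spans the whole absence, so the lack of an AE counterpart looks like an oversight. The same days may also enter the TE Period, exposure and compliance, depending on which document is followed and how one phrase is read.

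**Working it through.** **Step 1: follow an event through the rules.** Let an AE start after the other study's ETT visit.

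- *Resolved before the Returning Visit.* It did not occur within the other study, so the medical-history rule does not apply. It is not ongoing at return, so the second bridging rule does not apply. Collection restarts only at the Returning Visit. Under 13.1.1.3 it is not collected.
- *Ongoing at the Returning Visit.* It did not begin in the other study, so neither the bridging rule nor the SAP 9.3.1 flag reaches it. SAP Appendix C classifies by comparing onset with the TE Period. The SAP 9.1 TE Period runs from first dose in this study to 28 days after last dose (or completion, if earlier) without a break, so the onset lies inside it and the event would count as a TEAE although it began while the subject was away.

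**Step 2: how many days are involved.** The documents give no worked figure to reproduce. The planned treatment is 48 × 7 = 336 days (Protocol 9.3.2). Assumed for illustration: 100 dosed days before departure with immediate enrolment elsewhere, 50 days in the other study, a gap of g days, then 236 dosed days (100 + 236 = 336).

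Exposure = last dose day − first dose day + 1 − time in the other study. The span from first to last dose is 100 + 50 + g + 236 = 386 + g.

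- Reading A, time in the other study ends at its ETT visit: 386 + g − 50 = 336 + g.
- Reading B, it ends at the Returning Visit: 386 + g − (50 + g) = 336.

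| Gap g (days) | Exposure, A | Gap share, A | Exposure, B |
|---|---|---|---|
| 0 | 336 | 0% | 336 |
| 1 | 337 | 1/337 = 0.3% | 336 |
| 14 | 350 | 14/350 = 4.0% | 336 |
| 30 | 366 | 30/366 = 8.2% | 336 |
| 60 (needs approval) | 396 | 60/396 = 15.2% | 336 |

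**Step 3: TE Period at g = 30**, with a full 28 days after last dose.

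- Protocol, reading A: 366 + 28 = 394 days.
- Protocol, reading B: 336 + 28 = 364 days.
- SAP 9.1 as written: 416 + 28 = 444 days, which takes in both the 30-day gap and the 50 days in the other study.

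**Step 4: compliance at g = 30.** Under reading A, if gap days count as interruption, 100 × (1 − 30/366) = 91.8%. Under reading B the gap contributes nothing.

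**The case against.** Several points on the other side have weight.

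- *Collection may be continuous.* Table 3-1 and the general SAE rule in 13.1.2.2 run from consent to the end of participation. That conflicts with the specific rule in 13.1.1.3 and does not settle it. Protocol 9.1.2 and 9.1.5 also let a Departing Visit stand in for follow-up and mark completion, so even continuous collection may end at departure.
- *Some SAEs remain reportable.* Protocol 13.1.2.2 says "SAEs that occur after completion of study participation and are considered related to study drug(s) will be recorded on the Vertex Clinical Trial Safety Information" form. That could reach the gap if departure counts as completion, but only for related SAEs.
- *Persisting events are unlikely to be missed.* This stands: subjects are asked about AEs at every study visit. The clear loss is events that both start and end in the gap; for the rest, the defect is classification.
- *The gap may not count as exposure.* This stands too. Neither document says when time in the other study begins or ends, and the medication rule points towards reading B.

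A reader might infer two stronger points that the documents do not support. The first is that counted but unobserved days dilute AE frequency. AE tables give the number and percentage of subjects with an event (Protocol 12.3.4.1, SAP 9.3.1), with no exposure-adjusted rate, so extra days cannot dilute them; any understatement comes only from events not recorded. The second is that the 28-day limit for waiving follow-up after departure can be added, giving (30 + 28)/336 = 17.3%. AEs are collected up to enrolment elsewhere, so those days are not part of the uncollected interval.

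**Conclusion.** The point holds in a limited form. Under Protocol 13.1.1.3 and 13.1.2.2, an event that starts and resolves between the other study's ETT visit and the Returning Visit is not collected, and Table 3-1 contradicts that. An event ongoing at return is unclassified, and by onset date it falls in the SAP TE Period. Separately, SAP 9.1 lacks the exclusion that Protocol 12.3.1 makes, and the excluded time has no defined start or end.

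Per returner, the interval is 0 to 30 days without approval and longer with it. At 30 days it is 8.2% of counted exposure under reading A and nothing under reading B, given the illustrative assumptions. Only subjects who depart and return with a non-zero gap are affected. Their number and the other study's own follow-up are not in the documents, so the effect on pooled results cannot be computed. The study is descriptive and no test is at risk. The change is still worth making, because it improves capture on the only endpoint at little cost.

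**What to change.** 1. **Collection and class.** In Protocol 13.1.1.3, and by reference 13.1.2.2, collect at the Returning Visit all AEs and SAEs that began after the other study's ETT visit, whether resolved or ongoing. Reconcile this with Table 3-1. Extend the pre-treatment flag in SAP 9.3.1 to these events, so that they are listed as pre-treatment with off-treatment onset.
2. **Exposure and compliance.** In Protocol 12.3.2.4 and SAP 9.2.5 and 9.2.6, exclude the days between the last dose before departure and the first dose on resumption.
3. **TE Period.** In Protocol 12.3.1, and newly in SAP 9.1, exclude the time from enrolment in the other study (or from 28 days after the last dose before departure, if earlier) to the first dose on resumption. This boundary differs from item 2 on purpose: cutting the TE Period at the last dose would remove TEAE status from post-dose events that are collected before enrolment elsewhere.

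The cost is one retrospective question at a visit already held, plus wording changes in both documents. The downside is some recall-based AE data and slightly shorter reported exposure.
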